#### *Concomitant Medications*

14. Taking any other oral anti-diabetic agent other than Metformin, Insulin, Sulfanylureas and Meglitinide for their treatment of T2DM.

15. Beginning statin medications in the past 1 month or change in statin dose in the past 1 month
16. Use of consistent long-term steroid medication (oral, inhaled, injected) within the last 1 month
17. Treatment with a strong cytochrome P450 3A4 (CYP34A) or P-gp inducer (ie. Rifampin)
18. Subjects with a history of any serious hypersensitivity reaction to Dapagliflozin / Saxagliptin or another SGLT-2 inhibitor/ DPP4 inhibitor

*Laboratory Findings*

19. Uncontrolled hyperglycemia, defined as a fasting glucose  $>240$  mg/dL ( $>13.3$  mmol/L) at screening.
20. Liver disease with ALT, AST or ALP  $\times 3$  ULN
21. eGFR  $< 60$  mL/min/1.73 m^2 by MDRD equation in the past 3 months
22. Clinically significant RBC disorders such as hemoglobinopathies
23. Serum creatinine levels  $\geq 1.8$  mg/dL with estimated eGFP  $< 60$  mL/min
24. Triglycerides  $> 450$  mg/dL
25. Baseline Hematuria (judged by a urinalysis dipstick at screening)

*Social History*

26. Active smokers
27. Chronic or persistent alcohol or drug abuse
28. Prisoners or subjects who are involuntarily incarcerated
29. Subjects who are compulsorily detained for treatment of either a psychiatric or physical (eg. infectious disease) illness
30. Participation in another trial with an investigational drug within 30 days prior to informed consent

## 6 TREATMENT

### **STUDY TREATMENT: DAPAGLIFLOZIN AND DAPAGLIFLOZIN + SAXAGLIPTIN COMBO**

**Definition of Investigational Product:** A pharmaceutical form of an active substance or placebo being tested or used as a reference in a clinical study, including products already with a marketing authorization but used or assembled (formulated or packaged) in a way different from the authorized form, or used for an unauthorized indication, or when used to gain further information about the authorized form. In this protocol, the investigational products are Dapagliflozin, Saxagliptin, and their respective placebos.

This study is being conducted under FDA mandated guideline for use in type 2 diabetes. Though in this particular study Dapagliflozin and Saxagliptin are referred to as the investigational drug, they are not novel drugs and we should not need a separate IND for execution of this study.

**Definition of Non-Investigational Product:** Other medications used in the study as support or escape medication for preventative, diagnostic, or therapeutic reasons as components of a given standard of care. In this protocol, the non-investigational products are Metformin, Insulin, Sulfonylurea and Meglitinides. Patients will continue on their anti-diabetic therapy per their study entry dose. Doses may be altered if laboratory results indicate this is necessary.

### **METHOD OF ASSIGNING SUBJECTS TO A TREATMENT**

Subjects, as per selection criteria below will be randomized to treatments using a permuted block design, developed by the Epidemiology & Biostatistics Research Core. This approach ensures groups will be approximately balanced at any time during the study and at study completion. Randomization will be performed by the MFA IDS Pharmacy staff who never come in contact with subjects.

The recommended dose of Dapagliflozin is 10 mg PO will be given once daily in the Dapa group. The recommended dose of Saxagliptin 5mg along with Dapagliflozin 10 mg (one of each) will be given PO once daily in the Dapa+Saxa Combo group. Saxagliptin should be administered once daily with or without food, at any time of day. Dapa should be administered once daily with food, **in the morning**.

*Because of this, all subjects will be instructed to take their medication once daily in the morning with food, as we will not know which subjects will be in the Dapa, Dapa+Saxa Combo, or placebo group.*

### **DRUG DISPENSATION PLAN**

In order to maintain the blind, all subjects, regardless of which study group they are assigned to, will be taking a total of 2 pills orally each morning. Each pill will come from a separate bottle. Subjects in their respective groups will take the following each morning:

- **Dapagliflozin Group:** 1 active Dapagliflozin pill (Bottle A) **AND** 1 blinded Saxagliptin placebo pill (Bottle B)
- **Dapagliflozin + Saxagliptin Combo Group:** 1 active Dapagliflozin pill (Bottle A) **AND** 1 active Saxagliptin pill (Bottle B)
- **Placebo Group:** 1 blinded Dapagliflozin placebo pill (Bottle A) **AND** 1 blinded Saxagliptin placebo pill (Bottle B)

In order to help subjects remain compliant, and remember which bottle the took a pill from, they will be instructed to always take from the Dapagliflozin (or Dapa placebo) bottle, Bottle A, first. Both bottles will be labeled with some feature to clearly distinguish the two (ie. Colored labels, highlighting on the bottles, etc.)

### **DOSE MODIFICATIONS**

No dose modification is necessary for prior to CKD stage 3 (eGFR  $\geq$  60 mL/min/1.73 m^2). Treatment should not be initiated with an eGFR <60 mL/min/1.73 m^2. If the eGFR declines persistently between 30 to <60 mL/min/1.73 m^2 then treatment should be halted.

### **STUDY MATERIALS**

AstraZeneca (AZ) will provide the site with Dapagliflozin, Saxagliptin, a Dapagliflozin matching placebo, and a Saxagliptin matching placebo at no cost for this study. The placebo will be indistinguishable from its corresponding active drug, and will only be unblinded only to the site's research pharmacy.

### **MAINTAINING THE BLIND**

Blinding is critical to the integrity of this clinical study. However, in the event of a medical emergency or pregnancy in a subject, in which knowledge of the investigational product is critical to the subject's management, the blind for that subject may be broken.

Before breaking the blind of an individual subject's treatment, the investigator should have determined that the information is necessary, i.e., that it will alter the subject's immediate management. In many cases, particularly when the emergency is not investigational product-related, the problem may be properly managed by assuming that the subject is receiving active product without the need for un-blinding.

#### **END OF STUDY UN-BLINDING PROTOCOL**

Upon completion of the research study, we will undergo the following protocol in order to unblind the research data.

Unblinding is the process by which the allocation code is broken so that the investigator, clinical staff and the trial statistician becomes aware of which intervention each subject enrolled in the research study was taking.

Unblinding at the end of the study is required in order to make unmasked analysis in accordance with the study analysis plan. It is also conducted in order to inform the participants of which investigational product they were assigned to.

#### Time to unblind:

Unblinding shall be conducted when all subjects enrolled in the research study have finished treatment, and all follow up visits. There must be no plan to recruit any more subjects in the research study. Additionally, all data points and outcome measures for each research subject must have been collected, and ideally compiled. Prior to unblinding there will be a data lock on clinical outcome measures and basic side outcome measures and associated research data collected for the study.

#### Procedure to unblind

Once data (from both the clinical and the basic science side) and has been compiled and is data locked, the investigator can choose to unblind. The Principal Investigator must contact the study sponsor, and receive permission to un-blind. If, for unforeseen reasons, at the pre-determined date for full study unblinding the data analysis on the cellular or basic aspects of the study is lagging behind the clinical data outcome measures (though the data has been acquired) the Principal Investigator in consultation with the study sponsor may choose to un-blind the clinical outcome measures before the basic side data has been analyzed but compiled. Upon confirmation from the study sponsor, the principle investigator must make a written request to the designated party to unblind, hereto referred at the "unblinder". The unblinder is the bio-statistician of the MFA, **[name]**. Upon receipt of an instruction to unblind, the unblinder will sign the request form, indicating their agreement to unblind. This form will then be taken to the pharmacy, **MFA's IDS**, where a member of the IDS staff will take the form, and will give the unblinding study binder to the unblinder. The pharmacy will sign to indicate their release of the binder, and the unblinder will sign to indicate receipt of the binder. At this point in time the chain of custody of the pharmacy unblended binder has been transferred to the designated party to unblind. The form with all of the signatures will be provided to the study coordinator to be kept in the regulatory binder.

### **DISCONTINUATION OF SUBJECTS FROM TREATMENT**

Subjects **MUST** discontinue from the investigational product (and non-investigational product at the discretion of the investigator) for any of the following reasons:

- Withdrawal of informed consent (subject's decision to withdraw for any reason)
- Any clinical adverse event, laboratory abnormality, or inter-current illness which, in the opinion of the investigator, indicates that continued participation in the study is not in the best interest of the subject.
- Pregnancy
  - Pregnant patients will be advised to contact the investigator or study staff immediately if they suspect they might be pregnant (e.g. missed or late menstrual period) at any time during study participation.
- Loss of ability to freely provide consent through imprisonment or involuntary incarceration for treatment of either a psychiatric or physical illness (e.g. infectious disease).
- If ketoacidosis is suspected, promptly discontinue treatment.

**All subjects who discontinue should comply with protocol-specified follow-up procedures outlined before.** The only exception to this requirement is when a subject withdraws consent for all study procedures or loses the ability to consent freely (i.e., is imprisoned or involuntarily incarcerated for the treatment of either a psychiatric or physical illness). If a subject withdraws before completing the study, the reason for withdrawal must be documented appropriately.

## **7 ADVERSE EVENTS: DEFINITION + REPORTING**

**The Principal Investigator is responsible for ensuring that all staff involved in the study are familiar with the content of this section.**

### **Adverse Event (AE)**

An ***Adverse Event (AE)*** is defined as any new untoward medical occurrence or worsening of a pre-existing medical condition in a patient or clinical investigation subject administered an investigational (medicinal) product and that does not necessarily have a causal relationship with this treatment. An AE can therefore be any unfavorable and unintended sign (including an abnormal laboratory finding, for example), symptom, or disease temporally associated with the use of investigational product, whether or not considered related to the investigational product.

The causal relationship to study drug is determined by a physician and should be used to assess all adverse events (AE). The term "reasonable causal relationship" means there is evidence to suggest a causal relationship. The causal relationship can be one of the following:

- **Related:** There is a reasonable causal relationship between study drug administration and the AE.
- **Not related:** There is not a reasonable causal relationship between study drug administration and the AE.

Adverse events can be spontaneously reported or elicited during open-ended questioning, examination, or evaluation of a subject. (In order to prevent reporting bias, subjects should not be questioned regarding the specific occurrence of one or more AEs.)

Laboratory Test Abnormalities as AEs:

All laboratory test results captured as part of the study will be recorded following institutional procedures. Test results that constitute SAEs should be documented and reported as such.

The following laboratory abnormalities should be documented and reported appropriately:

- Any laboratory abnormality that required the subject to have study drug discontinued or interrupted
- Any laboratory abnormality that required the subject to receive specific corrective therapy.

Serious Adverse Event (SAE)

A *Serious Adverse Event (SAE)* is any untoward medical occurrence that at any dose:

- Results in death
- Is immediately life-threatening (defined as an event in which the subject was at risk of death at the time of the event; it does not refer to an event which hypothetically might have caused death if it were more severe)
- Requires inpatient hospitalization or causes prolongation of existing hospitalization (see note below for exceptions)
- Results in persistent or significant disability/incapacity
- Is a congenital anomaly/birth defect
- Is an important medical event that may jeopardize the subject or may require medical intervention to prevent one of the outcomes listed above. Examples of such events include but are not limited to intensive treatment in an emergency department or at home for allergic bronchospasm; blood dyscrasias or convulsions that do not result in hospitalization. Potential drug induced liver injury (DILI) is also considered an important medical event (see Section 7.6 for the definition of potential DILI)
- Suspected transmission of an infectious agent (e.g., any organism, virus or infectious particle, pathogenic or non-pathogenic) via the study drug is an SAE.
- Pregnancy, only where there is a suspicion that the investigational medicinal product may have interfered with the effectiveness of the contraceptive medication.
- Congenital abnormalities/ birth defects and spontaneous miscarriages.

**NOTE:** The following hospitalizations are **not** considered SAEs:

- A visit to the emergency room or other hospital department lasting less than 24 hours that does not result in admission (unless considered an “important medical event” or a life-threatening event)
- Elective surgery planned before signing consent
- admissions as per protocol for a planned medical/surgical procedure

- Routine health assessment requiring admission for baseline/trending of health status (e.g., routine colonoscopy)
- Medical/surgical admission for purpose other than remedying ill health state that was planned before study entry. Appropriate documentation is required in these cases.
- Admission encountered for another life circumstance that carries no bearing on health status and requires no medical/surgical intervention (e.g., lack of housing, economic inadequacy, caregiver respite, family circumstances, administrative).

### **Pregnancy**

If, following initiation of the investigational product, it is subsequently discovered that a study subject is pregnant or may have been pregnant at the time of investigational product exposure, including during at least 6 half-lives after product administration, the investigational product will be permanently discontinued immediately. Protocol-required procedures for study discontinuation and follow-up must be performed on the subject unless contraindicated by pregnancy (e.g., x-ray studies). Other appropriate pregnancy follow-up procedures should be considered if indicated.

If any pregnancy occurs in the course of the study, then the Investigator or other site personnel should inform the appropriate AstraZeneca representatives within 1 day, i.e., immediately, but **no later than 24 hours** of when he or she becomes aware of it.

Following initial AstraZeneca notification, the PI will ensure that all relevant information is provided to the AstraZeneca Patient Safety data entry site within 1 to 5 calendar days for SAEs and within 30 days all non SAE pregnancies.

The same timelines apply when outcome information is available.

### **Potential Drug-Induced Liver Injury**

Wherever possible, timely confirmation of initial liver-related laboratory abnormalities should occur prior to the reporting of a potential DILI event. All occurrences of potential DILIs, meeting the defined criteria, must be reported as SAEs as important medical events (see Section 7.2.1 for reporting details).

Potential drug induced liver injury is defined as

1. AT (ALT or AST) elevation > 3 times upper limit of normal (ULN)  
AND
2. Total bilirubin > 2 times ULN, without initial findings of cholestasis (elevated serum alkaline phosphatase),  
AND
3. No other immediately apparent possible causes of AT elevation and hyper-bilirubinemia, including, but not limited to, viral hepatitis, pre-existing chronic or acute liver disease, or the administration of other drug(s) known to be hepatotoxic.

### **Other Safety Considerations**

Any significant worsening noted during interim or final physical examinations, electrocardiograms, x-rays, and any other potential safety assessments, whether or not these

procedures are required by the protocol, should also be recorded as a AEs or SAEs (provided they meet the criteria for SAEs), as appropriate, and reported accordingly.

### **Adverse Event Collecting and Reporting**

The collection of adverse event (AEs / SAEs) information will begin after the signing of the informed consent. Adverse events can be spontaneously reported or elicited during open-ended questioning, examination, or evaluation of a subject. To prevent reporting bias, subjects should not be questioned regarding the specific occurrence of one or more adverse events. AEs will be followed to completion of the study, if considered not related, or until resolution or stabilization if considered related. They will be reported as SAEs if they become serious.

If known, the diagnosis of the underlying illness or disorder should be recorded, rather than its individual symptoms. The following information should be captured for all AEs: **onset, duration, intensity, seriousness, investigator causality to investigational product (yes or no), action taken, treatment required, and outcome**. If treatment for the event was administered, it should be recorded in the medical record. The investigator will report these to the IRB upon continuing review. The investigator must supply AstraZeneca and the IRB with any additional information requested.

### **Serious Adverse Event Collecting and Reporting**

Following the subject's written consent to participate in the study, all SAEs, whether related or not related to study drug, will be collected, including those thought to be associated with protocol-specified procedures. All SAEs will be collected that occur within 30 days of discontinuation of dosing or within 30 days of the last visit for screen failures. If applicable, SAEs will be collected that relate to any later protocol-specified procedure (e.g., a follow-up skin biopsy). The investigator will report any SAE occurring after these time periods that is believed to be related to study drug or protocol-specified procedure at 90 days and 180 days period. An SAE report will be completed for any event where doubt exists regarding its status of seriousness.

The following variables (if applicable) are recommended to be collected for SAEs: date AE met criteria for SAE, date PI became aware of SAE, seriousness criteria fulfilled, date of hospitalization, date of discharge, probable cause of death, date of death, whether an autopsy was performed, causality assessment in relation to study procedures, causality assessment in relation to other study medication, and description of SAE.

If the investigator believes that an SAE is not related to study drug, but is potentially related to the conditions of the study (such as withdrawal of previous therapy, or a complication of a study procedure), the relationship will be specified in the narrative section of the SAE Report Form. All SAEs, whether related or unrelated to Dapa or Saxagliptin, and all pregnancies will be reported to AZ (by the investigator or designee) **within 24 hours**.

The investigator must inform the FDA, via a MedWatch form, of any serious or unexpected adverse events that occur in accordance with the reporting obligations of 21 CFR 312.32, **and will concurrently forward all such reports to AstraZeneca**. A copy of the MedWatch report must be emailed to AstraZeneca (TCS vendor) at the time the event is reported to the FDA. It is

the **responsibility of the Investigator** to compile all necessary information and ensure that the FDA receives a report according to the FDA reporting requirement timelines and to ensure that these reports are also submitted to AstraZeneca at the same time.

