**Protocol Version: Version 1.1**

**May 06, 2019**

**Sponsor: The George Washington University Medical Faculty Associates**

**Funding Source: Astra Zeneca Pharmaceuticals, LP**

## PROTOCOL SYNOPSIS

Protocol Title:	Cardio-Protective Effect of Saxagliptin and Dapagliflozin Combination on Endothelial Progenitor Cells in Patients with Type 2 Diabetes
Site Numbers & Names	GWU Medical Faculty Associates
Research Hypothesis:	We hypothesize that Dapagliflozin will improve EPC number and function AND Saxagliptin in addition to Dapagliflozin (additive effect) may improve EPC number and function even more than Dapa alone, compared to placebo.
Study Schema: Drugs / Doses / Length of Treatment	
We propose a 3-arm randomized, parallel group, longitudinal study of 16-week intervention duration. Patients will be randomized to 3 groups:
 
Group A: Dapa (10 mg) + Saxa Placebo, Enroll n=15, retain n=12  Group B: Dapa (10 mg) + Saxa (5 mg), Enroll n=15, retain n=12  Group C: Dapa Placebo + Saxa Placebo, Enroll n=15, retain n=12
 
Total enroll 45, retain total 36

Study Objectives: 
 
• Primary
 
• Secondary
 
• Tertiary
 
	
Primary Outcome: Cellular Biomarker of Endothelium  The primary objective is to ascertain if 16 weeks of Dapa or Dapa+Saxa Combo therapy will improve CD34+ cell number, function and gene expression in type 2 diabetes with CVD.
 
Secondary Outcome: Arterial Stiffness and Renal Function, Non-Cellular Markers of Endothelium  The secondary objective is to determine whether use of Dapa or Dapa+Saxa Combo alters markers of endothelial function such as: arterial stiffness, blood biochemical measures pertaining to endothelial, renal function, and urine exosomes.
 
Tertiary Outcome: Metabolism Markers  The tertiary objective is to determine whether use of Dapa or Dapa+Saxa Combo alters body composition, fasting lipid profile, and levels of insulin, glucose, and appetite controlling hormones.

Study Design:	Prospective, double-blind, randomized placebo-controlled trial
Accrual Goal (Total number of subjects):	N = 45
Accrual Rate (Number of subjects expected per month):	Recruit 45 patients in approximately 20 months
Estimated Timeline:	FPPV: 06/01/2018 LPLV: 02/28/2020
Co-relative studies (PK/PD, etc.):	N/A

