## 4 INVESTIGATIONAL PLAN

### STUDY DESIGN AND DURATION

#### Enroll n=45 (15/group) for evaluable n=36 (12/group)

#### **+/- 6 day window for visits**

\*Assessed at week 0, 8 and 16: Primary, Secondary & Tertiary Outcomes.

Week 20: A telephone call to subjects will be made 4 weeks after last dose of study medication to determine if there have been any adverse events.

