## APPENDIX C: X CHART

	Phone Screening Screen Visit ing (Week - (Befor e week -2)	Baseline/ Randomization Visit 1 (Week 0)	During Treatment Visit 2 (Week 8)	End-of- Treatment Visit 3 (Week 16)	Follow up phone call (Week 20)
Informed Consent		X			
Inclusion / Exclusion Criteria	X	X			
Medical History		X			
Physical Examination		X			
Targeted Physical Examination (as needed)			X	X	X
Vital Signs		X	X	X	X
Assessment of Signs and Symptoms		X	X	X	X
Adverse Events Assessment			X	X	X
Laboratory Tests (Biochemical + Ketones)	Screening		X	X	X
Laboratory Tests (Bone Parameters)			X		X
Urine Pregnancy Test (As needed)		X	X	X	X
Spot Urine Sample			X	X	X
Waist/Hip Measurements			X	X	X
Body Composition Scale			X	X	X
Primary Outcome Measures			X	X	X
Secondary & Tertiary Outcome Measures			X	X	X
Randomize			X		
Dispense Study Treatment			X	X	

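### The last planned safety contact, 28 days after the last dose, comes 2 days before the 30-day SAE collection period ends

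*Combined protocol and SAP*

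**What the plan says.** Section 7, under Serious Adverse Event Collecting and Reporting, sets the period: "All SAEs will be collected that occur within 30 days of discontinuation of dosing". The sentence before it makes clear that this means related and unrelated events alike. For events after that period, the investigator reports only those "believed to be related to study drug or protocol-specified procedure at 90 days and 180 days period".

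Section 4 (Study Design and Duration) fixes the contact after treatment: "A telephone call to subjects will be made 4 weeks after last dose of study medication", labelled week 20, to find out whether there have been adverse events. The same section gives a plus-or-minus "6 day window for visits" and does not mention telephone calls. The synopsis describes a "longitudinal study of 16-week intervention duration", so weeks 16 and 20 are consistent with a 4-week interval. The last column of the schedule in Appendix C is "Follow up phone call (Week 20"; no later contact is listed.

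Section 7, under Adverse Event Collecting and Reporting, allows two routes: "Adverse events can be spontaneously reported or elicited during open-ended questioning".

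**The concern.** A commitment to collect every SAE for 30 days needs some planned occasion, at or after day 30, on which the patient is asked. The plan has one contact after treatment, and its stated date is day 28. What is at stake is the completeness of the SAE record against the protocol's own promise, chiefly for events judged unrelated. A related event that surfaces later still has a reporting route; an unrelated hospital admission on day 29 has none unless the patient calls the site. Entry requires existing cardiovascular disease or proteinuria (Section 5), so such admissions are plausible.

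**Working it through.** Inputs: SAE period 30 days after dosing stops (Section 7); end of treatment week 16 (synopsis); call at week 20, 4 weeks after the last dose (Section 4 and Appendix C); allowance of 6 days either side, worded for visits (Section 4). A call on day d is taken to cover events up to and including day d. The marks inside the Appendix C table are not legible enough to rely on, so only its column headings are used.

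1. The plan's own figure. Week 20 − week 16 = 140 − 112 = 28 days, which agrees with the stated 4 weeks.

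2. Gap at the planned date. Gap = 30 − d = 30 − 28 = 2 days. This needs no assumption about windows.

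3. Gap if the visit allowance covers the call (an assumption).
   - Permitted days: 28 − 6 = 22 to 28 + 6 = 34, which is 13 days.
   - Earliest call: 30 − 22 = 8 days uncovered, 8/30 = 27% of the period.
   - Days 22 to 29 (8 of 13): gap of 8 days down to 1.
   - Days 30 to 34 (5 of 13): no gap.

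4. Does the later reporting fill the gap? No. It applies only after the 30-day period, so it does not reach days 29 and 30, and it is limited to events thought related to the drug or a procedure.

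5. Scale. With the 36 patients the synopsis expects to retain, 2 days each is 36 × 2 = 72 person-days, or 72/365.25 = 0.20 person-years. The documents give no SAE rate. At an assumed 0.1 to 0.3 per person-year, that is 0.20 × 0.1 = 0.02 to 0.20 × 0.3 = 0.06 expected events. At the 8-day edge for every patient, 36 × 8 = 288 person-days, or 0.79 person-years, giving 0.08 to 0.24 events.

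**The case against.** The best case for the plan is that it promises collection, not questioning on day 30. Spontaneous reports are accepted, so an SAE on day 29 that the patient or a treating clinician reports is still collected. This stands: the gap is in active ascertainment only. It does not remove the point, because after the call nothing planned would bring an unvolunteered event to light.

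Second, if the 6-day allowance applies it works in both directions, and a call on days 30 to 34 leaves no gap. A reader might infer that the collection period always closes after the last contact. The documents do not support that; it is true at the stated date and on the earlier permitted days. Equally, the 8-day figure is a conditional extreme.

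Third, not all 45 enrolled patients are necessarily exposed to the gap. Section 6 asks patients who stop treatment early to keep to the follow-up procedures. If they keep the scheduled visits, a later contact will often fall beyond their day 30.

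Two stronger readings should be set aside. A reader might infer that the trial would publish 30-day SAE counts it did not ascertain; Section 9 plans no safety analysis and no such count. A reader might also think that the absence of a data safety monitoring board makes the gap worse. Such a board reviews accumulating data and does not contact patients after treatment, so its absence neither creates nor widens the gap.

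**Conclusion.** The mismatch is real and small. On the plan's own dates the last contact comes 2 days before the SAE period closes. That figure rests only on Sections 4 and 7 and the absence of any later contact in Appendix C. The range of 8 days to none holds only if the visit allowance extends to the call, which is not stated. The consequence is possible under-ascertainment of unrelated, unvolunteered SAEs, well below one expected event under the assumed rates. Sample size, power, type I error and the planned analyses are untouched. It merits correction because it bears on an explicit safety commitment and costs almost nothing to repair.

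**What to change.** Reconcile Section 4, Section 7 and Appendix C so that the existing call cannot fall before the SAE collection period closes, and say explicitly whether the visit allowance applies to it. For example, with the 30-day period as written, date the call at day 30 or later with no early allowance. If a 6-day early allowance were kept, the nominal date would have to be at least 30 + 6 = day 36. How long the SAE period should be is for the sponsor; the point is only that the places agree.

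The cost is the same call made 2 days later (8 days later if the early allowance is kept), with no added contact or staff. In the same edit, the sponsor could say how events are to be learned of in two other places where Section 7 sets a period with no scheduled contact: the 90- and 180-day reporting of related SAEs, and the collection "within 30 days of the last visit for screen failures".
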